## 3.2.6.2.1 Effect of timing of delivery on global ejection fraction

Evaluation of the influence of timing on global ejection fraction involves comparing the effect of BMMNC at the day three administration to the effect of BMMNC at the seven day administration. Assume the difference in the treatment effect is  $\delta = 5$ . The standard deviation of the change in ejection fraction from baseline to six months is 7.0. These as-

sumptions are based on the findings from the Wollert (24), Lunde (17), Schächinger (20), and Janssens (16) articles.

For this evaluation there is a 1:1 active patient to control patient allocation. We assume 5% of patients will be lost to follow-up based on our pilot trial results in 20 patients. From equation (1) the required sample size is 67 patients (rounded up to 68); 34 patients to the day three administration and 34 patients to the day seven administration.

The sensitivity of the sample size to different assumptions about the effect size and standard deviation of the difference are provided (Table 5.)

		Treatment Effect (δ)						
		4 5 6 7						
Std Dev	5	54	35	25	19	15		
of Diff	6	76	50	35	26	21		
(σ)	7	103	67	47	35	27		
	8	134	87	61	45	35		

**Table 5**.Total Sample Size for Effect of Timing on Global Ejection Fraction Type I error = 0.05; power = 80%; followup losses = 5%

## 3.2.6.2.2 Effect of timing of delivery on regional ejection fraction

Assessment of the influence of timing on regional ejection fraction involves comparing the effect of BMMNC at the three day administration to the effect of BMMNC at the seven day administration. Assume the difference in the treatment effect is  $\delta$  = 6.5. The standard deviation of the change in ejection fraction from baseline to six months is 9.5, conservatively rounded up to 10. These assumptions are based on the BOOST manuscript (18, 24). For this evaluation there is a 1:1 allocation. We assume 5% of patients will be lost to follow-up. From equation (1) the required sample size is 80 patients; 40 to the day three administration and 40 to the day seven administration. Examination of the sensitivity of the sample size to changes in the treatment effect and standard deviation of the difference assumptions follow (Table 6)

**Table 6**.Total sample size for effect of timing on regional ejection fraction Type I error = 0.05; power = 80%; followup losses = 5%

		Treatment Effect (δ)							
		4.5	4.5 5 5.5 6 6.5						
Std Dev	9	134	109	90	76	65			
of Diff	10	165	134	111	94	80			
(σ)	11	199	162	134	113	97			
	12	237	192	159	134	115			

In order to preserve power for each of these two evaluations, 80 patients will receive active therapy; 40 at the day three administration and 40 at the seven day administration.

## 3.2.6.3 Effect of BMMNC Infusion on global and regional ejection fractions

This evaluation compares the change in ejection fraction at baseline to six months in the active group to the change in the control group. In this evaluation, the effect of timing will not be considered, and patients at both the day three administration and the day seven administration can be combined, yielding 80 patients in the active group. Assuming a 2:1 active to placebo allocation, there will be 40 patients in the control group.

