#### 3.2.5 Stratification

Patients will be stratified by Clinical Center.

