#### 3.2.6 Sample size

The trial is a 2 x 2 factorial design (Table 3). The two factors are therapy (active versus placebo) and timing (three days versus seven days). Patients will be allocated in a 2:1 treatment versus placebo ratio at each of the two time points.

 Table 3. Cell Delivery and Timing

	Timing				
Placebo	3 Days	7 Days			
Active	3 Days	7 Days			

The questions this study is designed to answer are:

- 1. What is the effect of stem cell therapy on global and regional LV function when compared to placebo?
- 2. What is the influence of three day versus seven day cell delivery on the effect of BMMNC on global and regional LV function?

A total of 120 patients provide adequate power for an assessment of the overall effect of BMMNC administration to control in the six month change for each of global and regional ejection fraction, as well as permitting an adequately powered inquiry into the influence of timing on the effect of BMMNC for each co-primary endpoint (Table 4).

	Global	LVEF	Regiona	al LVEF
	Tim	ning	Tim	ning
Active	3 Days 40	7 Days 40	3 Days 40	7 Days 40
Placebo	40 20	40 20	20	40 20
1 lacebo	20	20	20	20

Table 4. Total sample size for global and regional LVEF

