## 5.5.1 Randomization to 3 Day versus 7 Day Administration

After the Clinical Center research team has determined that a patient satisfies the inclusion and exclusion criteria of the study and the patient has read and signed the informed consent, the Research Coordinator completes a secure form on the CCTRN web application. Completing this form validates that the patient has met the inclusion/exclusion criteria and acknowledges the informed consent has been completed. The patient's assignment to either three day or seven day administration is made at this point. The computerized randomization algorithm now assigns a study ID number to the patient. The assignment of therapy (i.e., active or placebo) occurs after bone marrow aspiration and cell processing (discussed in section 5.5.2).

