### 9.0 STATISTICAL PROCEDURES

#### 9.1 Randomization

Once informed consent has been obtained, eligible patients will be entered into the study randomly assigned to one of the selected treatment strategies in an interactive Web-based randomization session where exclusion and eligibility criteria will be assessed. Patients will be randomized to the time of administration (Day 3 or Day 7) using a variable block size of 4 or 6. Patients will be randomized to therapy type (active or control therapy), using variable block sizes of 3 or 6, randomly selected. Patients will be stratified by clinical center. When a patient is randomized, the clinic will be given an identification (ID) number and acrostic, specific information on the assigned treatment regimen, and a list of procedures to be completed at the baseline visit. A participantspecific schedule of visits and procedures will be displayed for printing locally. The DCC will monitor patient recruitment by providing reports to the Core Laboratories and Project Office (PO) as appropriate during the recruitment phase. Updated reports will be maintained on an Internet site accessible to all units of the study. The recruitment reports will provide data on recruitment of women and minorities (African-Americans, Hispanics, and Asians). Goals for recruitment will be set and will be reviewed by the DCC and PO.

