### 9.4.2 Co-primary endpoint evaluations

Each primary endpoint, global LVEF(%) and regional LV function is a continuous variable. General linear mixed modeling techniques will be utilized to assess the effect of treatment on the primary endpoint of the study. For patients recruited to the Day 3 arm of the study, the six month MRI will be compared to the Day 3 MRI. For patients recruited to the Day 7 treatment group, the six month MRI will be compared to the Day 7 MRI

The analysis variable will be the change in LVEF (either global or regional) from the immediate pre-infusion level to six months. Both unadjusted and adjusted treatment effects will be computed; adjustments will be for clinical site as well as for baseline covariates whose association with the dependent variable is generally accepted. In keeping with standard methodology for clinical trials, the primary analysis will compare the randomized study groups.

Despite the efforts of CCTRN Investigators to ensure that patients return to their center for follow-up evaluation, we anticipate that a small number of subjects will be unable to return for their follow-up endpoint assessment. Last observation carried forward analyses will be carried out as supportive evaluations.

Anticipating this difficulty, the sample size for this study has been increased by a small percent, allowing the Investigators to capture complete data on a number of patients as close to the pre-specified sample size as possible. However, for those patients who are missing the final six month endpoint data, we will carry out a Last Observation Carried Forward (LOCF) analysis. For a patient who is missing the follow up information, the value of the follow-up measure will be assumed to be equal to their base-line value. Thus the difference in the endpoint measure over the six month follow-up will be zero. While a large number of missing data points, corrected in this matter can produce a bias toward the null, this standard LOCF procedure will be adequate for the small number of patients with missing data.

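### The randomisation described does not secure the promised 2:1 allocation at each time point, and timing is not named in the co-primary model

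*Protocol*

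**What the plan says.** - **Allocation.** Section 3.2.6: "Patients will be allocated in a 2:1 treatment versus placebo ratio at each of the two time points". Table 4 sets the cells at 40 active and 20 placebo for each day.
- **Stratification.** Section 3.2.5: "Patients will be stratified by Clinical Center". Sections 4.2, 9.1 and 9.3 name the same factor. None of them names timing as a stratum for therapy.
- **Blocking.** Section 9.1 has two separate schemes: "Patients will be randomized to the time of administration (Day 3 or Day 7) using a variable block size of 4 or 6", and "Patients will be randomized to therapy type (active or control therapy), using variable block sizes of 3 or 6, randomly selected".
- **Order.** Timing is assigned at enrolment. Section 5.5.1: "The assignment of therapy (i.e., active or placebo) occurs after bone marrow aspiration and cell processing".
- **Power for the cell effect.** Section 3.2.6.3 combines the two days into 80 active and 40 placebo patients: "In this evaluation, the effect of timing will not be considered".
- **Analysis.** Section 9.4.2 uses general linear mixed models: "Both unadjusted and adjusted treatment effects will be computed". The adjustments are clinical site and accepted baseline covariates. Timing is neither named nor excluded. Change is taken from the Day 3 MRI in the Day 3 arm and from the Day 7 MRI in the Day 7 arm.
- **Does timing shift the change score?** Section 8.0 sets Day 3 as the baseline scan for everyone, because function often keeps recovering between Day 3 and Day 7. Section 3.2.6.2 assumes that placebo patients respond alike on either day.

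**The concern.** If therapy blocks run within a center but across its Day 3 and Day 7 patients, each block balances active against placebo in the center and leaves the split within each timing arm to chance. The 40/20 cells then become an average, which a given trial may miss by a wide margin. Allocation is fixed once patients are randomised, so a later analysis plan cannot restore it.

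The imbalance has consequences only if timing affects the outcome. On the protocol's own account it may: if function recovers between Day 3 and Day 7, a change measured from Day 7 starts higher and is smaller on average than one measured from Day 3. When the active and placebo groups then differ in their share of Day 7 patients, the pooled difference moves in that trial. If timing is also absent from the model, its variance stays in the residual.

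**Working it through.** **1. The plan's own power.** Inputs from sections 3.2.6.3.1 and 3.2.6.3.2: 80 active and 40 placebo, 5% loss (76 and 38 analysed); global δ = 5, SD 7; regional δ = 6.5, SD 10.

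Power = Φ(δ / (SD × √(1/76 + 1/38)) − 1.96), with √(1/76 + 1/38) = 0.19868.

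- Global: 5 / (7 × 0.19868) − 1.96 = 1.64, giving 94.9%, as stated.
- Regional: 6.5 / (10 × 0.19868) − 1.96 = 1.31, giving 90.5%. This matches Table 8; the text's 90.4% is the same figure at α = 0.0495.

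**2. Size of the timing-by-therapy cells.**

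- Simple approximation: of 120 patients, 40 are placebo and 60 are Day 3. The number of Day 3 placebo patients is hypergeometric with mean 20 and variance 60 × (1/3) × (2/3) × (60/119) = 6.72, so SD 2.59 and a 95% range of 15 to 25.
- Simulation of the block schemes: 10,000 trials of 120 patients; five centers of 19, 41, 19, 22 and 19, scaled from the enrolment projections in Table 13; timing blocks of 4 or 6; therapy blocks of 3 or 6; therapy assigned in date order.

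| | Therapy blocked by center | Therapy blocked by center and timing |
|---|---|---|
| Day 3 placebo cell, SD | 2.9 | 1.1 |
| 95% range | 14 to 26 | 18 to 22 |
| Day 3 active:placebo ratio, 95% range | 1.35 to 3.14 | 1.73 to 2.33 |
| Chance that either placebo cell is 16 or fewer | 22% | 0.1% |

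**3. Effect on the pooled estimate.** Take a 15/25 placebo split with 60 patients per day. The Day 7 share is 25/40 = 0.625 in placebo and 35/80 = 0.4375 in active, a difference of 0.1875. The protocol gives no size for the Day 3/Day 7 shift s in mean change, so a range of 0 to 5 points is assumed. The estimate moves by 0.1875 × s: 0 at s = 0, 0.75 at s = 4, 0.94 at s = 5. The standard error of the pooled global difference is 7 × 0.19868 = 1.39, so 0.94 is about two thirds of one standard error.

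**4. Effect on power of leaving timing out.** If the stated SD applies within a timing arm, a 50:50 factor with shift s raises it to √(SD² + s²/4).

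| s | Global SD | Global power | Regional SD | Regional power |
|---|---|---|---|---|
| 0 | 7.00 | 94.9% | 10.00 | 90.5% |
| 2 | 7.07 | 94.5% | 10.05 | 90.2% |
| 3 | 7.16 | 94.0% | 10.11 | 89.9% |
| 5 | 7.43 | 92.3% | 10.31 | 88.8% |

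If the stated SD is instead the total SD, the stated power stands without timing, and adding timing raises global power to at most 97.1% (s = 5).

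**5. Bias and type I error.** In 8,000 simulated trials per setting, with s from 0 to 5, the mean estimate was 5.0 for a true effect of 5, and type I error was 4.6% to 5.2%. At s = 5, simulated global power was 91.6% without timing and 94.1% with it.

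**6. The timing comparison.** At a 15/25 placebo split the active cells are 45 and 35. The effective size per arm is 2 × 45 × 35 / 80 = 39.4 against 40, so this test is barely affected.

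**The case against.** Four points can be made on the other side.

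**The sections can be read together.** Section 3.2.6 may imply that therapy is drawn within timing arm, which is feasible because timing is already known when therapy is assigned. That reading is possible, but section 9.1 is where the scheme is specified, and it does not say so. A programmer following 9.1 would build center strata alone.

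**The pooling sentence is not an analysis rule.** A reader might infer from section 3.2.6.3 that timing has been deliberately kept out of the primary model. The documents do not support that. The sentence explains which sample sizes enter a power formula, section 9.4.2 is silent on timing, and section 3.2.6.1 has timing assessed after the cell effect. Likewise, which of the unadjusted and adjusted estimates leads, and the full covariate list, are commonly left to an analysis plan and are not criticised here.

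**The shift is not documented.** Section 3.2.6.2 assumes none in controls. That stands, which is why a range starting at zero is used.

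**The shift comes largely from the baseline scan.** Using Day 3 for everyone, as section 8.0 describes, would remove the stunning-recovery part of it. This also stands: it weakens the case for the timing term, but leaves the allocation point untouched.

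**Conclusion.** The allocation point holds. The protocol promises 2:1 at each time point, and the scheme it describes delivers that only on average: about 14 to 26 in a placebo cell planned at 20, where blocking within timing would give about 18 to 22. These ranges rest on center sizes scaled from the recruitment projections.

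The model point holds in a milder form: timing is a randomised factor that the protocol itself gives reason to think prognostic for the change score, and section 9.4.2 does not name it.

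A reader might go on to conclude that the pooled cell-effect test is biased or invalid. It is not. Imbalance arises by chance, and its average effect over randomisations is zero. At the largest assumed shift the cost is 2.6 points of global power (94.9% to 92.3%) and 1.7 points of regional power (90.5% to 88.8%), and only if the stated SD is the within-timing SD. This is an inexpensive improvement in balance and precision and does not threaten the primary conclusion.

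**What to change.** 1. In section 9.1, state that the therapy list is generated within center and timing arm, keeping blocks of 3 or 6. With five centers this makes 10 strata and leaves a few incomplete blocks.
2. In section 9.4.2, include timing as a main effect in the model for both co-primary endpoints, with center and the baseline value of the endpoint. Timing is fixed before therapy is assigned, so it is a legitimate covariate. The cost is one degree of freedom and one line of text.
3. Reconcile sections 3.2.6.2, 8.0 and 9.4.2 on which scan is the baseline in the Day 7 arm, and on whether placebo patients are expected to differ by day.

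If enrolment has started, leave the allocation scheme as it is and make the model change alone. It needs no change to trial conduct and adjusts the pooled estimate for whatever timing imbalance has arisen.

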## 3.2.6.3.1 Effect of BMMNC infusion on global ejection fraction

Assume 80 active group patients and 40 control patients. We are assuming an absolute change  $\delta = 5$  and common group standard deviation of the difference of LVEF over time as  $\sigma(\Delta)_{LVEF} = 7$ , Type I error (two-tailed) = 0.0495. We anticipate that 5% of patients will be lost to follow-up. The standard deviation of the change in ejection fraction from baseline to six months is 7.0. These assumptions are based on the findings from the Wollert (24), Lunde (17), Schächinger (20), and Janssens (16) articles. Under these assumptions, the power is 94.9. A table displaying the sensitivity of the power computation to assumptions concerning treatment effect and standard deviation of the difference is provided (Table 7).

		Treatment Effect (δ)				
		4	5	6	7	8
Std Dev	5	0.981	0.999	1.000	1.000	1.000
of Diff	6	0.919	0.987	0.999	1.000	1.000
(σ)	7	0.820	0.949	0.991	0.999	1.000
	8	0.711	0.882	0.965	0.993	0.999

Table 7. Power for the effect of dose on lobal Ejection Fraction
Type I error = 0.05; N=120; 2:1 active:placebo ratio followup losses = 5%

## 3.2.6.3.2 Effect of BMMNC infusion on regional ejection fraction

Assume 80 active group patients and 40 control patients. We are assuming an absolute change  $\delta = 6.5$  and common group standard deviation of the difference of LVEF over time as  $\sigma(\Delta)_{LVEF} = 9.5$  conservatively increased to 10. These assumptions are based on the BOOST manuscript (18, 24). Type I error (two-tailed) = 0.0495. We anticipate 5% of patients will be lost to follow-up. Under these assumptions, the power is 90.4%. A table displaying the sensitivity of the power computation to assumptions concerning effect size and standard deviation of the difference is provided (Table 8).

		Treatment Effect (δ)				
		5	5.5	6	6.5	7
Std Dev	9	0.798	0.868	0.919	0.953	0.975
of Diff	10	0.711	0.791	0.855	0.905	0.941
(σ)	11	0.628	0.711	0.784	0.845	0.893
	12	0.555	0.636	0.711	0.778	0.835
		I				

**Table 8**.Power for the Effect of Dose on Regional Ejection FractionType I error = 0.05; N=120;2:1 active:placebo ratio: followup losses = 5%

A total of 120 patients provide adequate power for an assessment of the overall effect of BMMNC administration to control in the six month change for each of global and regional ejection fraction, as well as permitting an adequately powered inquiry into the influence of timing on the effect of BMMNC for each co-primary endpoint.

#### 3.2.6.4 The multiple testing issue

Type I error correction in the multiple testing environment can be useful protective devices, guarding against type I error inflation. Such tools are a staple of Phase III confirmatory studies. The use of this tool in Phase II "proof-of-concept-studies" is problematic. At this level of investigation, tight control of the overall family wise type I error rate would increase the likelihood that the Investigators would attribute a potentially important treatment effect to the play of chance. Nevertheless, Investigators must be cognizant that chance effects occur commonly in Phase II trials. The Investigators have tried to strike a balance between the need to control the number of evaluations and the need to identify new effects, on the other, by limiting the number of primary endpoints.

## **4.0 SELECTION AND ENROLLMENT OF SUBJECTS**

To carry out this study 120 patients are required. Patients enrolled in this study will be recruited from all of the sites participating in the National Heart, Lung, and Blood Institute (NHLBI) CCTRN. Patients with an acute MI are admitted to the respective hospitals of the Network or transferred from local hospitals affiliated with the Network hospitals. All patients will have undergone percutaneous revascularization of the infarct artery that has resulted in a moderate to large infarction with an LVEF  $\leq$  45% by echocardiography. All prospective patients will be screened by the Investigators and study coordinators and will be enrolled in the trial after meeting inclusion/exclusion criteria and signing both the informed consent and HIPAA form.

## 4.1 Implantable Cardiac Defibrillator (ICD) Use

In 40 patients enrolled to date in our preliminary study, we have had no patients meet criteria for ICD/bi-ventricular pacemaker (Bi-V) therapy. One patient had an ICD placed for palpitations and light-headedness, which was presumed to be ventricular in origin but never documented. All patient's LVEF have been greater than 35% at three months

and no patients have had ventricular arrhythmias (sustained or significant nonsustained) by Holter Monitoring or symptoms such as syncope. All patients with documented ventricular tachycardia (VT) or non-sustained VT on Holter monitoring or with syncope during the trial will be referred to an electrophysiologist for evaluation of the potential need for ICD placement. If a patient in the trial requires an ICD/Bi-V before the scheduled six month cMRI than cMRI will be performed just prior to implantation. However, the patient's measurements of global LVEF from entry into the study until completion will be assessed by echocardiography in place of cMRI.

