#### 2.2.1.1 Preliminary Results

Forty patients (31M, 9F) with moderate to large anterior infarctions have enrolled in the trial to date. Their average age is 54 years and seven have non-insulin dependent diabetes mellitus (NIDDM). Their average ischemic time is 7.2 hrs and seven have required intra-aortic balloon pump (IABP) support. Two patients underwent hypothermia treatment following initial cardiac arrest. The average day of transplant was five ± two days following their MI. The peak creatine kinase (CK) was 3074 IU and the CKMB was 282 IU. Their average LVEF by echocardiography performed one day following their MI was 37%. Their average LVEF by cMRI was 48% performed three to five days following their MI. In the Minneapolis Heart Institute, the LVEF by cMRI is 10% higher than that measured by echocardiography. All patients had significant MVO on their baseline MRIs. Their average LVEDV was 189.5 ml and left ventricular end systolic volume (LVESV) was 102.9 ml with an initial LV mass of 173 grams.

The average bone marrow aspirate collection was 65 ml and the mean BMMNC number was 170 million cells. The average percent  $CD34^+$ ,  $CD133^+$  and  $CD34^+/CD133^+$  cell TNC count in the delivered cell product was 2.01%, 0.22% and 1.09% respectively. The viability of the isolated BMMNC was greater than 96% in all patients.

Four significant adverse events were reported during the trial. One patient in the placebo group received an ICD for palpitations and syncope. One patient in the BMC group underwent CABG 8 months following cell therapy for an anomalous right coronary artery that was found to course between the aorta and pulmonary artery. One patient in the placebo group underwent repeat stenting in the LAD for in-stent restenosis at 15 months followed by CABG one month later after admission for a NSTEMI due to stent thrombosis. One patient in the BMC group underwent stenting of the circumflex artery two months following cell therapy infusion due to a pre-existing stenosis. There were no serious, unexpected, events that were related or possibly related to the study product or procedure reported during the trial.

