## 6.2 Consent Visit (Day 0 to Day 2)

- Consent signed
- Inclusion / Exclusion Review
- Complete Medical History and Medication Review
- Physical Exam, including vital signs, height, weight and pulse oximetry
- Laboratory Tests (include complete blood count (CBC/diff, lipid panel, renal panel, hepatic panel, troponin I or T, CK, CK-MB, hsCRP, BNP level, and pregnancy test (women of childbearing age))
- Assays for the detection of HIV and HCV (by nucleic acid testing), anti-HIV I/II, anti-HTLV I/II, anti-HBc antibody (Ab), HBsAg, anti-HCV, and Treponema pallidum (by serology) are collected per local site's standard operating procedure.\*
- Echocardiogram (LVEF <45%) (send to echo core lab following study product randomization)\*
- 12 lead ECG

¥ Infectious disease testing can be done on Day 3.

NOTE: The treatment checklist must be completed and submitted prior to the bone marrow aspiration. Subjects who fail the checklist will be excluded from the study.

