### **8.0 ENDPOINT EVALUATION AND CLASSIFICATION**

A cardiac MR 1.5 T scanning unit (Avanto, Cardiac MR Scanner, Siemens Medical Systems or equivalent) will be used for cardiac MR images. The exact cMRI Scanner will vary at each institution, however, the exact imaging protocols will be established by the MRI Core Lab. cMRI was chosen by the Network to evaluate the primary and secondary endpoints because it is independent of the geometric assumptions required for calculations of ejection fraction compared to echocardiography or left-ventriculography. Furthermore, the inter-study reproducibility for cMRI is significantly better than echocardiography for measurements such as LVEF, LVEDV, LVESV and cardiac mass (36, 37). However, the patient's measurements of global LVEF from entry into the study until

completion will be assessed by echocardiography in place of cMRI when MRI is contraindicated.

A series of scout images will be required with a pulse sequence that collects an image in a fraction of the RR interval. Scout imaging will start with a transverse view at the mid-ventricular level. Using the first scout as a localizer, the technologist will acquire the next scout image for the image plane that intersects with the long axis of the LV. A horizontal long axis cine series (four chamber view) will be acquired first followed by the long axis cine (twp chamber view). The image planes for the short axis studies will start at the base of the heart, at least two cm above the mitral-tricuspid valve plane to achieve maximal LV coverage. Using Tru-FISP (balanced- FFE) cineangiography, the slices will be consecutively positioned every 7 mm from the base to apex with a 3 mm interslice gap. The acquisition window for retrospectively-triggered cine sequence will be obtained. End-expiratory breath-hold with sampling throughout the entire cardiac cycle will be employed because of better reproducibility of each slice position for more accurate left ventricular volume analysis. A minimum of 20 cardiac phases will be used to cover the RR interval. All patients will undergo baseline cMRI measurements at Day 3 given that resolution of myocardial stunning and improvement in global and regional LV function often continues to occur between Day 3 and Day 7 which would negatively bias the Day 7 group when LV function is reanalyzed at six months.

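### Patients who become MRI-ineligible have global LVEF change measured from the Day 0–2 qualifying echo, which conflicts with the pre-infusion cMRI baseline in Section 9.4.2; the expected effect is small

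*Protocol*

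**What the plan says.** **The switch.** Section 4.1 deals with a patient who needs an ICD or bi-ventricular pacemaker before the six-month scan. It first orders a last scan: "cMRI will be performed just prior to implantation". It then says that the patient's "measurements of global LVEF from entry into the study until completion will be assessed by echocardiography in place of cMRI". Section 8.0 repeats the rule without a time limit: "completion will be assessed by echocardiography in place of cMRI when MRI is contraindicated". Because the switch runs from entry, it replaces the baseline as well as the follow-up value.

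**The echoes available.** Sections 6.2 to 6.9 and Table 11 schedule echo at the consent visit (Day 0 to Day 2) and at month 6. Month 12 and 24 echoes are added only if MRI becomes contraindicated. The infusion visit (Section 6.3) lists cMRI and no echo. The consent-visit entry reads "Echocardiogram (LVEF <45%) (send to echo core lab following study product randomization", so this is the scan on which the LVEF limit of 45% (Sections 3.1 and 4.0) is judged.

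**The endpoint.** Section 9.4.2 defines the analysis variable as the change in LVEF "from the immediate pre-infusion level to six months" and names the Day 3 or Day 7 MRI as comparator. It makes no exception for echo. Section 3.2.2 says that both co-primary endpoints are measured by cMRI.

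**The concern.** For switched patients the stated rule and the stated endpoint cannot both be followed. Following the switch has three consequences.

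- **Earlier baseline.** Section 8.0 itself says that function often goes on improving between Day 3 and Day 7 as stunning resolves, and that baseline timing can bias the comparison. A Day 0–2 echo is earlier still, so recovery before infusion is counted as change after it.
- **Selected baseline.** The baseline value is the one that had to fall at or below 45%. Some of the later rise is then regression to the mean. The cMRI baselines of the other patients are not selected on their own value.
- **Better measurements set aside.** Section 8.0 calls cMRI significantly more reproducible than echo. The baseline cMRI and the pre-implant cMRI are nevertheless not used for global LVEF.

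Contraindication to cMRI is an exclusion (Section 4.5), so these switches arise after entry. In Section 4.1 the path to a device is ventricular tachycardia or syncope, which could differ by arm. A different rule for just these patients could then move a co-primary comparison.

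**Working it through.** **1. The plan's own figure.** Section 3.2.6.3.1 uses an effect of 5, SD 7, 80 active and 40 control patients, and 5% loss. Evaluable numbers are 80 × 0.95 = 76 and 40 × 0.95 = 38. The standard error is 7 × √(1/76 + 1/38) = 1.39. Power is Φ(5/1.39 − 1.96) = 0.949, which agrees with the stated 94.9. At the two-sided 0.0495 given in the text it is also 0.949 (0.9485). These figures only anchor the scale.

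**2. Lead time of the echo baseline at nominal days.**

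| Arm | Infusion | Consent echo | Gap |
|---|---|---|---|
| Day 3 | 3 | 0 to 2 | 1 to 3 days |
| Day 7 | 7 | 0 to 2 | 5 to 7 days |

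The gap is longer in the Day 7 arm, so the timing comparison is exposed as well.

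**3. Regression to the mean.** The protocol gives no screening distribution. Assume screened echo LVEF with mean 48, SD 10 and test-retest correlation (ICC) 0.7 to 0.9.

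- Formula: (1 − ICC) × SD × φ(c)/Φ(c), with c = (45 − 48)/10 = −0.3 and φ(c)/Φ(c) ≈ 1.0.
- ICC 0.9, 0.8, 0.7 give 1.0, 2.0, 3.0 points.
- Wider assumptions (mean 40 to 50, SD 8 to 10, within-patient SD 3 to 5) give about 0.5 to 3.9 points.

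**4. Stunning recovery.** The documents do not isolate it. The pilot (Section 2.2.1.1) reports 37% by echo on day 1 and 48% by cMRI on days 3 to 5, and says that at that centre "the LVEF by cMRI is 10% higher than that measured by echocardiography". Read as EF points, this leaves 48 − 37 − 10 = 1 point, with modality and time confounded. Read as a relative 10%, it leaves 48 − 37 × 1.10 = 7.3 points.

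**5. Shift in the treatment contrast.** Let B be the extra change created by the early echo baseline. B is not given, so take 1 to 10 points, a range that covers both readings in step 4. Shift = (number switched in the arm / evaluable in the arm) × B.

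| Switched | All active (of 76) | All placebo (of 38) | Balanced |
|---|---|---|---|
| 3 (pilot 1/40 × 120) | +0.04 to +0.39 | −0.08 to −0.79 | 0 |
| 12 (10%, assumed) | +0.16 to +1.58 | −0.32 to −3.16 | 0 |

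For the timing contrast, 3 switched patients all in the active Day 7 group (38 evaluable) shift it by 0.08 to 0.79.

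**6. Power under balanced switching.** With a fraction f switched, SD = √((1 − f) × 49 + f × SD_echo² + f(1 − f)B²). With SD_echo assumed at 7 to 10 and two-sided alpha 0.0495, power is 0.933 to 0.948 at f = 2.5% and 0.886 to 0.948 at f = 10%.

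**7. Scope of the rule.** Section 4.1 covers devices before month 6. Section 8.0 has no time limit; read literally, it would replace a valid six-month cMRI in a patient who becomes ineligible later. The Table 11 footnote implies echo only from that time on. The three statements differ.

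**The case against.** **Keeping one modality is sensible.** With a stated offset of 10 points, a six-month echo set against a cMRI baseline would build in a large error. A constant offset cancels echo to echo. This stands: the fault lies in which echo serves as baseline and in the unused cMRIs, not in avoiding a mixture.

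**The pilot figures do not measure the inflation.** A reader might infer from 37% and 48% that switched patients gain some 11 points. The documents do not support that, because the figures come from two modalities and the stated offset, read as points, accounts for most of the gap.

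**Few patients are affected.** One of 40 pilot patients received an ICD, and Section 4.1 says that none met device criteria and that all had LVEF above 35% at three months. This also stands, with one reservation: the pilot admitted LVEF below 50% (Section 2.2.1), so the rate could be higher under a 45% limit.

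**Core-lab reading.** The consent echo goes to the core lab after randomisation. An independent re-reading could remove reader-related regression, but not day-to-day variation or stunning.

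**Regional function.** A reader might infer that the cMRIs are thrown away and that regional data are lost. The switch names global LVEF only. The pre-implant cMRI can still give a regional value; only the six-month regional value is lost.

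**Conclusion.** The inconsistency is in the text: for MRI-ineligible patients, Sections 4.1 and 8.0 impose a baseline for global LVEF that Section 9.4.2 does not allow. That baseline is exposed to early recovery and to selection at 45%.

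The likely size is small. At the pilot device rate about 3 patients switch, and the shift stays below 0.8 points against a planned effect of 5 and a standard error of 1.39, even with all of them in one arm and B = 10. It reaches 1.6 (all active) or 3.2 (all placebo) only if 10% switch, all in one arm, with B = 10. Balanced switching gives no mean shift.

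A reader might infer that the rule favours cell therapy. The documents do not support a direction: the inflation favours whichever arm has more devices, and nothing says which that would be. The regression figure rests on an assumed screening mean, SD and ICC, and B is an assumed range. The case for change is that a co-primary endpoint's rule contradicts its definition and can be put right with scans already ordered.

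**What to change.** Reconcile Sections 4.1 and 8.0 with Section 9.4.2 as follows.

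1. The primary analysis of global LVEF uses cMRI only. The baseline is the pre-infusion cMRI named in Section 9.4.2, which must itself be reconciled with the statement in Section 8.0 that all patients have their baseline at Day 3.
2. The pre-implant cMRI is kept as an observed value, and a six-month cMRI that cannot be done is treated as missing in the mixed model. The text should say how the off-schedule scan enters, since a single change score has no place for it.
3. Echo-to-echo change is reported as a sensitivity analysis.
4. Section 9.4.2 assigns zero change to patients without six-month data. For these patients, state that the supportive LOCF analysis carries the pre-implant cMRI forward instead.
5. Give Sections 4.1 and 8.0 and the Table 11 footnote the same scope, so that a valid six-month cMRI is not replaced when MRI becomes contraindicated afterwards.

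**Cost.** No new scan or patient is needed; the change is to wording and to the model specification. A few patients will lack a direct six-month value in the primary analysis, which then relies on the missing-data assumption of the mixed model for them.
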